10.7. Appendix 7: List of Data Displays

10.7.1. Data Display Numbering

The following numbering will be applied for RAP generated displays:

Section	Tables	Figures
Study Population	1.1 to 1.8	NA
Efficacy*		
Safety	3.1 to 3.5	NA
Section	Listings	
ICH Listings	1 to 21	
Other Listings	22 to 24	

*Will be provided by Martinos

10.7.2. Study Population Tables

Study Population: Tables					
No.	Population	IDSL / TST ID / Example Shell	Title	Programming Notes	Deliverable [Priority]
Subject Disposition					
1.1.	Safety	ES1A	Summary of Subject Disposition for the Subject Conclusion Record		SAC
1.2.	Screened	ES6	Summary of Screening Status and Reasons for Screen Failures		SAC
Demography					
1.3.	Safety	DM1	Summary of Demographic Characteristics		SAC
1.4.	Enrolled	DM11	Summary of Age Ranges		SAC
1.5.	Safety	DM5	Summary of Race and Racial Combinations		SAC
1.6.	Safety	DM6	Summary of Race and Racial Combination Details		SAC
1.7.	Enrolled	NS1	Summary of Number of Subjects Enrolled by Country and Site ID		SAC
1.8.	Enrolled	SP1A	Summary of Study Population		SAC

10.7.3. Efficacy Tables

All Efficacy tables and listings will be provided by Martinos.

10.7.4. Safety Tables

Safety: Tables					
No.	Population	IDSL / TST ID / Example Shell	Title	Programming Notes	Deliverable [Priority]
3.1.	Safety	AE16	Summary of Serious Adverse Events by System Organ Class and Preferred Term (Number of Subjects and Occurrences)		SAC
3.2.	Safety	AE15	Summary of Common ($\geq 2\%$) non-serious Adverse Events by System Organ Class and Preferred Term (Number of Subjects and Occurrences)		SAC
3.3.	Safety		Vital Signs of Clinical Concern by Visit		SAC
3.4.	Safety		Summary of GI- VAS		SAC
3.5.	Safety		Summary of MSAQ		SAC

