In both Part A and Part B, subjects who meet the eligibility criteria will be randomized in a crossover fashion to one of 4 different sequences, each consisting of two dosing/imaging sessions (Session 1 and Session 2) separated by a 6-9-week washout period (Section 4.2 Table 1). Each subject will undergo a single off-therapy MRI during a separate Visit according to the randomization sequence to minimize the total number of scans per subject. The timing or sequencing of the off-therapy MRI will be randomized (i.e. Session 1 or Session 2) to account for potential learning effects. Each subject will undergo one off-therapy MRI, one post-dose albiglutide MRI and one post-dose exenatide MRI for a total of 3 MRI scans during the study. The visit schedule is set to allow the Off-therapy MRI scan visit to occur approximately 7 days prior to the post-dose scan within the Session as this is the minimal recommended time between scans. The visit on Day 5 allows the dosing of albiglutide or albiglutide placebo to occur 4 ± 1 days before the post-dose MRI i.e., at estimated T_{max} (3-5 days). Because of the short T_{max} (2 hrs) for exenatide, exenatide or saline placebo is given on the day of the MRI scan (Day 8). Therefore, MRI Session 1 and Session 2 each consist of 2 or 3 single-day out-patient visits according to the randomization schedule on the following days:

- Day 1 (Either Session 1 or 2 per randomization) for an off-therapy MRI scan consisting of resting-state fMRI, a nauseogenic task fMRI, ASL and MRS and nausea associated assessments,
- Day 5 for a single dose of 50 mg albiglutide or albiglutide placebo, and
- Day 8 for a single dose of 10 μ g exenatide or saline placebo followed by a post-dose MRI scan consisting of resting-state fMRI, ASL and MRS, and nausea associated assessments.

Subjects will be blindfolded when receiving the study medication injection to maintain the single-blind.

For all MRI sessions, subjects must fast overnight and will be instructed to refrain from eating and drinking anything but water starting at approximately 10 pm the night before or with in 8 hours of the start of their MRI appointment.

For the off-therapy session, MRI scan and nausea associated assessments will be conducted without prior injection (no drug, no placebo).

On post-dose scanning visits, subjects will be offered a meal after the procedure before leaving the unit, and capillary glycemia will be assessed.

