- h. All MRI include resting-state fMRI, ASL and MRS. Off-therapy MRI scan includes visual nauseogenic task fMRI and can be initiated once -assessments are completed. The on-therapy scan should be initiated 1 hr ±15min post the exenatide or exenatide placebo dose. Pre-scan procedure timings are suggested times to allow completion of activities. Post MRI procedure should be completed at the noted times ±15 min.

- i. MSAQ is given following the VAS.
- j. Subjects will be offered a snack prior to leaving the site.
- k. Only events related to the Study Procedures meeting the SAE criteria are reported after screening and before dose on Session 1 Day 5.
- l. Subjects should remain at the site for at least 1 hr after completion of MRI. All procedures and assessments must be complete prior to discharge. The Investigator will approve the release of the subject from the clinic, or will provide treatment for the standard of care as required.
- m. The Post-dose MRI **MUST** be scheduled 4 ± 1 days after the albiglutide or albiglutide placebo dose. The day of dosing albiglutide is counted as the first day.

Procedure	Screening		Session 1						Wash out	Session 2						F/U							
	Week -4 to -1		Day 1	Day 4±1 ^m					6-9 weeks	Day 1			Day 5±1 ^m	Day 8±1 ^m					Week 13				
	1	2		-2h	-0.5h	0h	0.5h	1h		Post MRI	Pre-MRI	MRI		Post MRI	0.5h	1h	-2h	-0.5h		0h	0.5h	1h	Post MRI
Visit (all out-patient)	1	2	3	4							5			6	7					8			
Dosing albiglutide or placebo ^g			X									X											
Dosing exenatide or placebo ^g					X											X							
MRI ^h								X			X								X				
Autonomic monitoring								X			X								X				
Electrogastrogram								X			X								X				
VAS						X		X			X	X				X			X				
MSAQ ⁱ								X			X								X				
Capillary blood glucose								X											X				
Fasting Plasma Glucose								X											X				
Snack ^j								X			X								X				
AE assessment ^k			X	←-----→							←-----→			X	←-----→					X			
Discharge ^l								X				X							X				X

- a. Medical history includes alcohol/tobacco/caffeine usage.
- b. Prior-Medications are defined as prescription or over-the counter medications taken within 30 days of Screening. Record concomitant medications and or changes
- c. WCBP is women of child-bearing potential. Serum pregnancy test at Screening. Urine pregnancy at other specified time points
- d. If test otherwise performed within 1 month prior to first dose of study treatment, testing at screening is not required

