8.2.2. Vital Signs

The vital sign summary and analysis will include systolic blood pressure (mmHg), diastolic blood pressure (mmHg), and heart rate (bpm).

For Part A, each vital sign parameter at every scheduled assessment time point will be summarized using descriptive statistics. Additionally, the number of subjects with vital signs of potential clinical concern will also be summarized. The criteria for vital signs of potential clinical concern are detailed in [Appendix 7: Values of Potential Clinical Importance](#).

All summaries will be done for the safety population and all vital sign data will be listed.

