10.3. Appendix 3: Assessment Windows**10.3.1. Definitions of Study Day**

When study day is used for display or in comparisons the following algorithm will be used:

- Study day = date of assessment – date of first dose + 1, if day of assessment \geq first dose date
- Study day = date of assessment – date of first dose, if day of assessment < first dose date

Note that the date of first dose is Day 1 and the day before the date of first dose is Day -1 (there is no Day 0).

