10.7.5. ICH Listings

ICH: Listings					
No.	Population	IDSL / TST ID / Example Shell	Title	Programming Notes	Deliverable [Priority]
1	Safety	CP_TA1	Listing of Randomised and Actual Treatments		SAC
2	Safety	ES3	Listing of Reasons for Study Withdrawal		SAC
3	All Screened	ES7	Listing of Reasons for Screening Failure		SAC
4	Enrolled	SA3a	Listing of Subjects Excluded from Any Populations		SAC
5	Safety	DV2	Listing of Important Protocol Deviations		SAC
6	Safety	IE3	Listing of Subjects with Inclusion/Exclusion Criteria Deviations		SAC
7	Safety	DM2	Listing of Demographic Characteristics		SAC
8	Safety	DM10	Listing of Race		SAC
9	Safety	EX3	Listing of Exposure		SAC

ICH: Listings					
No.	Population	IDSL / TST ID / Example Shell	Title	Programming Notes	Deliverable [Priority]
10	Safety	AE7	Listings of Subject Numbers for Individual Adverse Events		SAC
11	Safety	AE9	Listing of All Adverse Events		SAC
12	Safety	AE9	Listing of Serious Adverse Events		SAC
13	Safety	AE9	Listing of Adverse Events Leading to Withdrawal from Study / Permanent Discontinuation of Study Treatment		SAC
14	Safety	AE7	Listing of subjects who withdrew from study due to Adverse Event		SAC
15	Safety	LB5	Listing of Clinical Chemistry Laboratory Data for Subjects Abnormalities of Potential Clinical Importance		SAC
16	Safety	LB5	Listing of Haematology Data for Subjects with Abnormalities of Potential Clinical Importance		SAC
17	Safety	UR2b	Listing of Urinalysis Data		SAC
18	Safety	EG3	Listing of 12 lead ECG Values		SAC
19	Safety	CP_VS4	Listing of Vital Signs for Subjects with Abnormalities of Potential Clinical Importance		SAC
20	Safety	LB5	Listing of all Haematology Data		SAC
21	Safety	LB5	Listing of all Chemistry Data		SAC

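### The only listed vital-sign table is by visit, which does not identify drug or condition in this crossover, and the descriptive table and full listing promised in SAP 8.2.2 are missing from the display list

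*SAP*

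**What the plan says.** SAP 10.7.4 lists one vital-sign table, Table 3.3, "Vital Signs of Clinical Concern by Visit". Its shell and programming-note cells are blank.

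SAP 8.2.2 promises more. It says "each vital sign parameter at every scheduled assessment time point will be summarized using descriptive statistics", adds a count of subjects with values of potential clinical concern, and closes with "All summaries will be done for the safety population and all vital sign data will be listed". It does not say that vital signs are shown by treatment, although 8.2.4 says so for adverse events. The only vital-sign listing in SAP 10.7.5 is Listing 19, "Listing of Vital Signs for Subjects with Abnormalities of Potential Clinical Importance".

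SAP 10.5.1 gives two display descriptors, albiglutide and exenatide. Off-therapy has none. SAP 10.3.1 defines study day from a single origin ("Note that the date of first dose is Day 1 and the day before the date of first dose is Day -1"), to apply "When study day is used for display or in comparisons the following algorithm will be used".

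Under Protocol 4.1 and Table 1 of 4.2, both the drug order and the session holding the off-therapy scan are randomised. Protocol 7.1 therefore has two schedules. SAP 10.2.1 reproduces only the one with the off-therapy scan in Session 1.

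**The concern.** Vital signs are a secondary endpoint for the safety and tolerability of each drug (SAP 2.2). In a crossover, a per-drug display has to carry the drug, or the off-therapy state, and the time relative to dosing. Here the visit label carries neither, because one visit number is a different kind of visit in different sequences. A table arranged only by visit could put no-drug, placebo and on-drug values in one row.

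The missing displays make this worse. If programming follows Appendix 7 rather than 8.2.2, a change on drug that crosses no concern limit would appear in no listed vital-sign display unless the subject was flagged for another value.

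**Working it through.** No sample size, power or error rate is involved. The check sets the passages side by side and adds simple day arithmetic.

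**Step 1. Condition at each visit number.** Inputs are the four sequences (Protocol 4.2, Table 1) and the visit order in the two schedules (Protocol 7.1; SAP 10.2.1). In the available text, the schedule with the off-therapy scan in Session 1 shows visit numbers 1, 2, 4, 6 and 8; Visits 3, 5 and 7 are inferred from order.

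| Visit | Sequence 1 | Sequence 2 | Sequence 3 | Sequence 4 | Distinct states |
|---|---|---|---|---|---|
| 3 | off-therapy scan | albiglutide injection | off-therapy scan | placebo pen | 3 |
| 4 | albiglutide injection | albiglutide on board + saline, scan | placebo pen | exenatide, scan | 4 |
| 5 | albiglutide on board + saline, scan | off-therapy scan | exenatide, scan | off-therapy scan | 3 |
| 6 | placebo pen | placebo pen | albiglutide injection | albiglutide injection | 2 |
| 7 | exenatide, scan | exenatide, scan | albiglutide on board + saline, scan | albiglutide on board + saline, scan | 2 |

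All five visits mix states. Off-therapy occurs only at Visits 3 and 5, and no single visit holds off-therapy, placebo and both drugs.

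**Step 2. Would treatment columns be enough?** Suppose each session is assigned to its active drug.
- Visits 6 and 7 separate cleanly.
- At Visit 4 the albiglutide column still combines injection day (sequence 1) with the scan near expected Tmax (sequence 2). The exenatide column combines the placebo-pen visit, before that session's exenatide (sequence 3), with the exenatide scan (sequence 4).
- Off-therapy values at Visits 3 and 5 have no descriptor of their own.

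**Step 3. Promised against listed.**

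| SAP 8.2.2 | Appendix 7 |
|---|---|
| Descriptive statistics at each scheduled time point | no table |
| Count of subjects with values of concern | Table 3.3 |
| Listing of all vital-sign data | only Listing 19, subjects with abnormalities |

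Chemistry and haematology each have both an abnormal-values listing (15, 16) and a full listing (21, 20). The vital-sign gap therefore looks like an oversight. As an illustration, a heart rate rising from 65 to 110 bpm stays below the concern limit of 120 bpm (SAP 10.4.2). With no other flagged value for that subject, it would appear in no listed vital-sign display.

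**Step 4. Study day, if it is used.** Take nominal days without windows, with Day 1 as the first injection of the study.
- Sequences 3 and 4: the exenatide scan is on Day 4. Sequences 1 and 2: Day 4 is the albiglutide scan.
- Exenatide scan in sequences 1 and 2, with the 6 to 9 weeks measured between dosing scans (Protocol 4.1): 4 + 42 = Day 46 to 4 + 63 = Day 67.
- If the washout instead runs from the Session 1 scan to the first Session 2 visit, that visit falls on Day 46 to 67. The scan is 3 days later in sequence 1 (Day 49 to 70) and 7 days later in sequence 2 (Day 53 to 74).

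On either reading, study day does not align a drug across sequences.

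**The case against.** A reader might infer that no drug effect on vital signs can be read from the planned output. The documents do not support that.
- A by-visit title does not exclude treatment columns. The adverse-event table titles also omit treatment, yet 8.2.4 puts those events by treatment group. SAP 10.5.1 supplies two descriptors, and the safety population is based on treatment actually received. The plan is silent on treatment for vital signs; it does not prescribe pooling.
- With four subjects, Listings 1 and 9 give each subject's treatments and exposure, so any listed value can be assigned by hand.
- The imaging centre is also to provide heart rate and blood pressure.
- Protocol 4.1 names visits by function. If Table 3.3 used those names, off-therapy would have its own row and treatment columns would resolve the rest.

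Most of this stands, within limits. Table 3.3 does not say which meaning of visit applies, and the schedules number the visits. Assigning values by hand works only for values that are listed, and Appendix 7 lists vital signs only for flagged subjects. SAP Attachment 11 says the autonomic data will not be available from every scan.

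Two other inferences also fail. The study-day rule is conditional and does not drive a by-visit table. The concern limits serve a different purpose from the entry criteria, so their distance from those criteria is not a defect shown here.

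**Conclusion.** The point holds as a defect of display. Visit alone identifies neither drug nor exposure time at any of Visits 3 to 7. Neither 8.2.2 nor Table 3.3 adds treatment, and treatment columns alone would leave Visit 4 mixed if visits are numbered. The mismatch between 8.2.2 and Appendix 7 is a plain internal contradiction and does not depend on how visit is read.

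The size is modest. SAP 2.1 describes four completed subjects and a decision not to complete group analysis, so the consequence is the descriptive clarity of the per-drug safety display.

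The mapping assumes that visit means the schedule's visit number, including the numbers inferred from order. How much mixing occurs depends on the sequences the four subjects received, which the documents do not state. The study-day figures are nominal and depend on the washout reading.

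**What to change.** 1. In 8.2.2 and Table 3.3, present vital signs by condition (off-therapy, albiglutide session, exenatide session) and nominal time point within the session: the pen-injection visit, or time relative to the Day 8 or Day 4 injection and scan.
2. Add an off-therapy display descriptor to 10.5.1.
3. Add to Appendix 7 the descriptive vital-sign table and the full vital-sign listing, both labelled by condition.
4. Where a day is displayed, add a session-relative day beside study day, with the same anchor for both drugs. The date of that session's pen injection, albiglutide or placebo, would serve. Under the rule in 10.3.1, the scan becomes 8 − 5 + 1 = Day 4 (or 4 − 1 + 1 = Day 4), and off-therapy becomes 1 − 5 = Day −4, in every sequence. Anchoring on the active dose would instead put the exenatide scan on Day 1 and the albiglutide scan on Day 4.

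The cost is SAP wording, one table, one listing and one derived variable. No new data are needed.

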10.7.5. ICH Listings

ICH: Listings					
No.	Population	IDSL / TST ID / Example Shell	Title	Programming Notes	Deliverable [Priority]
1	Safety	CP_TA1	Listing of Randomised and Actual Treatments		SAC
2	Safety	ES3	Listing of Reasons for Study Withdrawal		SAC
3	All Screened	ES7	Listing of Reasons for Screening Failure		SAC
4	Enrolled	SA3a	Listing of Subjects Excluded from Any Populations		SAC
5	Safety	DV2	Listing of Important Protocol Deviations		SAC
6	Safety	IE3	Listing of Subjects with Inclusion/Exclusion Criteria Deviations		SAC
7	Safety	DM2	Listing of Demographic Characteristics		SAC
8	Safety	DM10	Listing of Race		SAC
9	Safety	EX3	Listing of Exposure		SAC

ICH: Listings					
No.	Population	IDSL / TST ID / Example Shell	Title	Programming Notes	Deliverable [Priority]
10	Safety	AE7	Listings of Subject Numbers for Individual Adverse Events		SAC
11	Safety	AE9	Listing of All Adverse Events		SAC
12	Safety	AE9	Listing of Serious Adverse Events		SAC
13	Safety	AE9	Listing of Adverse Events Leading to Withdrawal from Study / Permanent Discontinuation of Study Treatment		SAC
14	Safety	AE7	Listing of subjects who withdrew from study due to Adverse Event		SAC
15	Safety	LB5	Listing of Clinical Chemistry Laboratory Data for Subjects Abnormalities of Potential Clinical Importance		SAC
16	Safety	LB5	Listing of Haematology Data for Subjects with Abnormalities of Potential Clinical Importance		SAC
17	Safety	UR2b	Listing of Urinalysis Data		SAC
18	Safety	EG3	Listing of 12 lead ECG Values		SAC
19	Safety	CP_VS4	Listing of Vital Signs for Subjects with Abnormalities of Potential Clinical Importance		SAC
20	Safety	LB5	Listing of all Haematology Data		SAC
21	Safety	LB5	Listing of all Chemistry Data		SAC

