5.3. Screening/Baseline/Run-in Failures

Screen failures are defined as subjects who consent to participate in the clinical trial but are never subsequently randomized. In order to ensure transparent reporting of screen failure subjects, meet the Consolidated Standards of Reporting Trials (CONSORT) publishing requirements, and respond to queries from Regulatory authorities, a minimal set of screen failure information is required including Demography, Screen Failure details, Eligibility Criteria, and Serious Adverse Events. Subjects can be rescreened once if agreed after discussion with the Medical Monitor.

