7.4.1.1. Time period and Frequency for collecting AE and SAE information

- Any SAEs assessed as related to study participation (e.g., protocol-mandated procedures, invasive tests, or change in existing therapy) or related to a GSK product will be recorded from the time a subject consents to participate in the study up to and including any follow-up contact.
- AEs will be collected from the start of Study Treatment until the follow-up contact, at the timepoints specified in the Time and Events Table (Section 7.1).
- Medical occurrences that begin prior to the start of study treatment but after obtaining informed consent may be recorded on the Medical History/Current Medical Conditions section of the CRF.
- All SAEs will be recorded and reported to GSK within 24 hours, as indicated in [Appendix 3](#).
- Investigators are not obligated to actively seek AEs or SAEs in former study subjects. However, if the Investigator learns of any SAE, including a death, at any time after a subject has been discharged from the study, and he/she considers the event reasonably related to the study treatment or study participation, the Investigator must promptly notify GSK.

NOTE: The method of recording, evaluating and assessing causality of AEs and SAEs plus procedures for completing and transmitting SAE reports to GSK are provided in [Appendix 3](#).

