4. ANALYSIS POPULATIONS

Population	Definition / Criteria	Analyses Evaluated
All Screened	
 • All participants who were screened will be considered for this population. This population will be used for summarizing screening status 	
 • Screen failure
Enrolled	
 • All participants who were successfully screened and enrolled for the trial and for whom a record exists on the study database. 	
 • Study population
Safety	
 • Comprise of all subjects who receive at least one dose of study treatment. • This population will be based on the treatment the subject actually received. • This population will include subjects who were replaced due to imaging data being invalid or not evaluable but received study drug. 	
 • Safety
Analysis Set (Randomised)	
 • Comprise of all randomized subjects who receive treatment and with valid imaging data, that will be determined by Martinos. • Subjects who are replaced are excluded from this population. 	
 • Imaging (Mechanism of Action)

NOTES :

- Please refer to Appendix 7: List of Data Displays which details the population to be used for each display being generated.

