10.7.6. Non-ICH Listings

Non-ICH: Listings					
No.	Population	IDSL / TST ID / Example Shell	Title	Programming Notes	Deliverable [Priority]
22	Analysis		Listing of GI- VAS		SAC
23	Analysis		Listing of MSAQ		SAC
24	Analysis		Listing of MRI		SAC

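### SAP Appendix 7 leaves an SAE in a never-dosed subject out of every display, and lists GI-VAS and MSAQ on a narrower population than it tabulates them

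*SAP*

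**What the plan says.** **SAE collection.** Protocol Section 7.4.1.1 says that SAEs related to study participation or to a product of the sponsor "will be recorded from the time a subject consents to participate in the study up to and including any follow-up contact". For screen failures, Protocol Section 5.3 says that "a minimal set of screen failure information is required including Demography, Screen Failure details, Eligibility Criteria, and Serious Adverse Events". Footnote k to the Time and Events tables (Section 7.1) adds that procedure-related SAEs are reported between screening and the first dose.

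**SAE display.** SAP Section 4 defines the Safety population with the words "Comprise of all subjects who receive at least one dose of study treatment", and its note sends the reader to Appendix 7 for the population of each display. There, Table 3.1 (SAE summary) and Listing 12 ("Listing of Serious Adverse Events") are both labelled Safety. SAP Section 8.2.6 promises a listing of deaths and SAEs and names no other population. Section 8.2.1 makes Safety the default.

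**GI-VAS and MSAQ.** SAP Sections 1 and 2.2 treat both as safety and tolerability endpoints. Table 3.4 ("Summary of GI- VAS") and Table 3.5, its MSAQ counterpart, use Safety. Listing 22 ("Listing of GI- VAS") and Listing 23 (MSAQ) use 'Analysis'. No population has exactly that name. The nearest is the Analysis Set (Randomised), defined as "Comprise of all randomized subjects who receive treatment and with valid imaging data, that will be determined by Martinos", which leaves out replaced subjects. Of the Safety population, by contrast, Section 4 says: "This population will include subjects who were replaced due to imaging data being invalid or not evaluable but received study drug". Protocol Section 9.2.2 likewise keeps replaced subjects' data for safety analysis and for nothing else.

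**The concern.** This study makes people feel sick on purpose before it gives them any drug. Every subject meets the visual stimulus in the mock scanner during screening (Protocol Section 7.2.3). Subjects in sequences 1 and 3 meet it again in the scanner on Day 1, ahead of first dosing on Day 5 (Sections 4.1 and 4.2). Protocol Section 7.4.1 exempts nausea during the task from AE reporting but requires other untoward events to be reported. If such an event is serious and the subject goes no further, the protocol has it recorded but the SAP has nowhere to show it.

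The second mismatch touches the tolerability data. Excessive head motion is a named ground for excluding imaging data (Protocol Section 9.2.2). A subject made restless by nausea is a plausible candidate for invalid imaging, and that subject's own nausea scores would then be missing from the by-subject listing. The table and the listing of the same endpoint would not reconcile.

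**Working it through.** No sample size, power or error rate is involved. The check is to read each display's population label against the population definitions and the protocol's collection rules.

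**1. Can any display show an SAE in a never-dosed subject?**

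| Displays (SAP Appendix 7) | Population | Content, by title |
|---|---|---|
| Tables 3.1, 3.2; Listings 10 to 14 | Safety | AEs and SAEs |
| Table 1.2; Listing 3 | Screened / All Screened | Screening status, reasons for screen failure |
| Tables 1.4, 1.7, 1.8 | Enrolled | Age ranges, counts by country and site, study population |
| Listing 4 | Enrolled | Exclusions from populations |

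Seven displays deal with adverse events (2 tables + 5 listings), and all seven require a dose. The six that can include an undosed subject (4 tables + 2 listings) do not deal with SAEs. Displays that would show the event: 0.

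**2. Who is outside the Safety population?** Protocol Section 4.3 plans about 10 screened for 4 randomised in Part A. If all 4 are dosed, about 10 − 4 = 6 screened subjects fall outside Safety, or 6/10 = 60%. Anyone randomised and not dosed adds to that. This is the planned number to whom the gap could apply, not a number of SAEs.

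**3. The randomised but undosed subject.** The SAP's copy of the Time and Events table places randomisation in the screening period. Protocol Section 5.4 allows withdrawal on the day of the off-therapy MRI, which in sequences 1 and 3 precedes any dose. Such a subject:
- is not a screen failure, because Section 5.3 reserves that term for those never randomised, so Listing 3 does not apply;
- is not in Table 1.1 (disposition) or Listing 2 (withdrawal reasons), both on Safety;
- would be named in Listing 4 as excluded from a population, but without the reason for withdrawal.

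**4. GI-VAS and MSAQ.** For a subject who was dosed and then replaced, or whose imaging was judged invalid:

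| | Table 3.4 or 3.5 (Safety) | Listing 22 or 23 ('Analysis') |
|---|---|---|
| Dosed, valid imaging, not replaced | in | in |
| Dosed, invalid imaging | in | out |
| Dosed, replaced | in | out |

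The last two rows are the mismatch. The documents do not say how many subjects fall there; the number is zero if all imaging was valid and nobody was replaced.

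**The case against.** The case on the other side has several parts.

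- **No display rule is broken.** A reader might infer that the protocol requires these SAEs to be tabulated or listed. It does not. Sections 5.3 and 7.4.1.1 govern what is collected and reported to the sponsor, and neither prescribes a table. Under Section 7.4.1.1 and footnote k, pre-dose SAEs are also limited to related ones. This stands: the gap lies between data collected and data displayed.
- **A by-treatment table should stay on dosed subjects.** SAP Section 8.2.4 summarises AEs by treatment group, and Section 10.5.1 provides only albiglutide and exenatide as descriptors. An undosed subject has no column. This stands, and it is why Table 3.1 is left alone.
- **The nausea data are not lost.** Tables 3.4 and 3.5 keep every dosed subject's scores, and AEs of nausea in dosed subjects remain in Listing 11. Only by-subject lines go missing. The 0–4 nausea rating comes from the imaging laboratory with no population stated (SAP Section 8.2.7), so the point concerns GI-VAS and MSAQ only. This stands.
- **The MRI listing is a different matter.** A reader might infer that Listing 24, also on 'Analysis', wrongly hides failed scans. The documents do not support that. Protocol Section 9.3.1 restricts the analysis set to valid data, Section 9.2.2 keeps replaced subjects out of anything but safety analysis, and SAP Section 8.2.1 permits exceptions to its default. The content of the listing is not described.
- **The loss may be nil.** SAP Section 2.1 reports four completers, and no document shows an invalid scan, a replacement or an undosed randomised subject. A reader might infer a fixed percentage loss from one bad scan; the documents give no basis for any such figure.

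None of this removes the two mismatches.

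**Conclusion.** The point holds on two counts. Followed as written, Appendix 7 shows an SAE in a never-dosed subject in none of its displays, and the withdrawal reason of a randomised, undosed subject is also absent. GI-VAS and MSAQ listings can omit dosed subjects whom their own tables include, against the protocol's rule that replaced subjects' data serve the safety analysis.

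The size is modest. The effect is limited to displays; 24-hour SAE reporting to the sponsor (Protocol Section 7.4.1.1) is unaffected, so it would be wrong to infer that an SAE would go unreported to the sponsor. In the four Part A completers the practical effect may be zero. The point should be corrected because correction is nearly free, not because it threatens a conclusion of the study.

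Three assumptions carry it: that 'Analysis' means the Analysis Set (Randomised); that display content is as the titles say, since no shells are shown; and that the Appendix 7 labels are applied literally.

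**What to change.** In SAP Appendix 7:

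- Keep Table 3.1 on Safety.
- Run Listing 12 on All Screened with pre-treatment events flagged, or leave it on Safety and add one SAE listing for undosed subjects.
- Set Table 1.1 and Listing 2 to Enrolled.
- Set Listings 22 and 23 to Safety, to match Tables 3.4 and 3.5.

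The last change has a limit. A subject in sequence 1 or 3 who stops undosed after the Day 1 vection scan will have GI-VAS and MSAQ scores that still appear in neither table nor listing. The change makes the two agree; it does not extend them to undosed subjects.

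The cost is a few population labels plus one flag or one short listing, with a label for subjects who received no treatment. The protocol already calls for the underlying data.
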